to investigate patients' adherence with diseases of the global airways, and analyse whether patients' adherence with diseases of the global airways can be improved and whether this will contribute to increased disease control and significantly improved quality of life.

Purpose

To investigate the effect of systematic and structured nursing guidance in patients with global airways disease, CRSwNP and asthma primarily on adherence (measured on MARS-5- L/N), where the maximum score is 50 at 100% adherence for both diseases. As well as whether there is a change at the minimum in adherence in patients who receive systematic and structured guidance on disease and treatment compared to usual care which does not include structured guidance.

Hypothesis and research questions

Patients with respiratory diseases can improve their adherence to their non-medical and the medical treatment for CRSwNP/CRS and asthma by systematic and structured nursing guidance compared to patients who did not receive the above guidance.

In a randomized study, we will investigate whether the level of adherence measured by the questionnaire MARS-5-N and MARS-5-L in patients with CRSwNP/CRS and asthma can be improved by 5 points after systematic and structured nursing guidance at baseline visit and controlled after four months - compared with those patients who have not received the above guidance.

Outcomes

The primary outcome is to investigate whether the adherence rate measured by the MARS-5-N/L questionnaire in patients with CRSwNP and asthma can be improved by 4 points after systematic and structured nursing guidance at the initial visit and controlled after four months - compared with those patients who have not received the above guidance.

Secondary outcomes

- To demonstrate whether improved adherence can improve their sleep measured on a Epworth Sleepiness Scale - messured during a 4 month follow-up visits.

- To demonstrate whether improved adherence can improve their SNOT22 score by 9 points or more messured at a 4 month follow-up visits.

- To demonstrate whether improved adherence can improve their asthma control as measured by the ACQ messured at a 4 month follow-up visits.

- To demonstrate whether improved adherence can improve their asthma control as measured by ACT - measured at a 4 months follow-up visit.

- To demonstrate whether improved adherence can improve their quality of life as measured by the mini AQLQ messured at a 4 months follow-up visit.

06.05.2022

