The study is a randomized trial with a control group and an intervention group. Patients will be randomized via Research Electronic Data Capture (Redcap), a secure web application for building and managing databases and online questionnaires. The system was developed at Vanderbilt University, which released the first version in 2008 (22). Patients will be randomized to the control or intervention group. Randomization will be stratified by gender. Patients in the intervention group will receive systematic and structured nursing guidance regarding their adherence, which includes proper use of nasal irrigation once or twice daily, nasal steroid/drops, use of inhaled medications, follow-up of smoking status. The intervention group will receive guidance videos which have been prepared prior to the study and will be standard for the intervention group. Guidance videos will cover the correct use of nasal irrigation, inhalation steroid, and nasal steroid/drops. The control group and intervention group will receive twice a week text message reminders to take their medications and to rinse their nose.

Their adherence will be measured via MARS-5-N and MARS-5-L f. Total MARS-5-N/L will be measured at their initial visit and four months after teaching or usual care. The same form will be given at both visits. Patients in the control group will not receive systematic and structured nursing care regarding their adherence, but their adherence will be measured via MARS-5-N and MARS-5-L max score is 50 when measuring a adherence in global airways. In a pilot study, mean (SD) 20.4 (6.28) is found for MARS-5-L, and for MARS-5-N mean 20.7 (5.57) is found. 41 points correspond to 80% of total of both MARS-5-L and MARS-5-N. A satisfactory adherence should be 80%. In another pilot study, patients were measured twice with at least one month in between. Here, the mean of the inter-individual difference at MARS-5-L/N first and second time is equal to 5.34(2.62). These two pilot studies will be used for the final power calculation.

Statistics data analysis and power calculation

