The statistical analysis of data is performed using IBM SPSS Statistics. Results will be presented as mean, SD, range and 95% CI. The parametric data will be compared using paired and unpaired tests, and non-parametric data using Wilcoxon Signed-Ranks Test and Mann-Whitney Test, respectively. Categorical variables are tested by chi-square test. A P-value <0.025 is considered significant for a pooled MARS-5-N and MARS-5-L For a pooled MARS5-L/N questionnaire, the total score would be 25x2= a total of 50 points theoretically. A safe difference is calculated from the intraindividual difference detected in the pilot study (mean 5.34 (2.62)), but based on the pilot study an SD and mean are calculated on the difference between MARS-5-L/N, which corresponds to an SD 5.34 and mean 2.62. With a MIREDIF of 5 and the largest SD of 6.28 by single measurement with a p-value of 0.025% (0.05/2) because there are two schedules and a power 80%, this would require 36 patients in each group including a dropout of 20%.

In addition, ensuring that MARS-5-N/L are both above 80% (the standard requirements for good adherence); and hoping for 100% adherence in the intervention group, versus 80% in the control group, this would require 39 in each group. - And including the 20% dropout rate, the total population would be 47 in each group.

Project participants

[name], nurse, Department of Otolaryngology and Audiology

[name], clinical nurse specialist and ph. Student, Department of Ear, Nose and Throat Surgery and Audiology

[name], Senior Physician, Department of Ear, Nose and Throat Surgery and Audiology

[name], Professor, MD, Department of Ear, Nose and Throat Surgery and Audiology

Risks and side effects

There are no serious side effects associated with participation in the trial. There may be a risk that patients in the control group of the study may have a worse prognosis/prognosis than patients achieving good adherence (80%) in the intervention group. To reduce this risk, patients in the control group are offered the same guidance as those in the intervention group at the end of the trial.

Information from patient records

No personal data will be collected from patient records. Data included in the study are from patient questionnaires and from results of clinical objective tests.

Processing of personal data

The project is carried out in compliance with the Data Protection Regulation and the Data Protection Act.

Economy

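### The four-month MARS-5 depends on a visit, and the 20% expected loss is met only by a larger sample; a remote link for non-attenders would cheaply reduce the exposure to bias

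*Combined protocol and SAP*

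**What the plan says.** Material and method in the combined protocol and SAP fixes the timing of the primary measure: "Total MARS-5-N/L will be measured at their initial visit and four months after teaching or usual care". It continues: "The same form will be given at both visits". The Outcomes section asks whether adherence "can be improved by 4 points after systematic and structured nursing guidance at the initial visit and controlled after four months", and most of the secondary questionnaires are placed at a four-month follow-up visit.

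Dropout appears only in Statistics data analysis and power calculation. The first calculation concludes that "this would require 36 patients in each group including a dropout of 20" per cent; the second goes from 39 to 47 per group with the same allowance. That section lists paired and unpaired tests, their rank counterparts and the chi-square test. It names no analysis population, no method for missing scores and no sensitivity analysis. No section says how a form would be sought from a patient who withdraws or misses the visit.

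Three other statements bear on the remedy. Owning and being able to use a smartphone is an entry condition (Population and recruitment). Both arms are texted twice a week (Material and method). REDCap, used for randomisation, is described as "a secure web application for building and managing databases and online questionnaires".

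**The concern.** The outcome is how well patients keep to treatment, so staying away from follow-up may well be related to the score that goes unrecorded. The arms also differ in ways that could affect return: only one receives nurse guidance and videos, and the other is offered the same guidance when the trial ends (Risks and side effects).

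The listed tests use, by default, only patients with a four-month form. The randomised comparison then becomes a comparison of attenders. Enrolling more patients restores precision, but it does not remove a bias of this kind. Once the four-month window has passed, the missing scores cannot be recovered.

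**Working it through.** **1. The plan's own figures.** Inputs from the statistics section: "With a MIREDIF of 5 and the largest SD of 6.28 by single measurement"; 80% power; level 0.025. The level is printed once as a percentage but shown as 0.05/2, and the analysis rule reads "A P-value <0.025 is considered significant for a pooled MARS-5-N and MARS-5-L". Sidedness is not stated; two-sided reproduces the figures.

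- Means: n = 2 × (2.241 + 0.842)² × (6.28/5)² = 30 per group; 30 × 1.2 = 36, as stated.
- Proportions, 100% versus 80%, unpooled: n = (2.241 + 0.842)² × 0.16/0.04 = 38.02, so 39; 39 × 1.2 = 46.8, so 47, as stated.

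Dropout therefore enters only as a multiplier on the sample size. With 20% lost, 36 × 0.8 = 28.8 or 47 × 0.8 = 37.6 per group remain.

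**2. Formula for the bias.** Let d be the share of an arm without a form, and gap the mean of those with a form minus the mean of those without. The mean of those with a form exceeds the full-arm mean by d × gap. So

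bias in the difference (intervention minus control) = d_I × gap_I − d_C × gap_C.

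**3. Scenarios.** The overall 20% is the plan's; the split by arm and the gaps are assumptions.

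| Loss, intervention / control | Gap, intervention / control | Bias (points) |
|---|---|---|
| 20% / 20% | equal | 0 |
| 20% / 20% | 5 / 0 | +1.0 |
| 20% / 20% | 0 / 5 | −1.0 |
| 30% / 10% | 6.28 / 6.28 | 0.20 × 6.28 = +1.26 |
| 10% / 30% | 6.28 / 6.28 | −1.26 |

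The target is 4 points in Outcomes and 5 points in the hypothesis and the power calculation: 1.26/5 = 25% and 1.26/4 = 31%.

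**4. Scale.** The 6.28 is the pilot SD of MARS-5-L, a 25-point scale; the endpoint is the 50-point total, whose SD is not given. From the pilot SDs 6.28 and 5.57, the SD of the sum is √(6.28² + 5.57²) = 8.4 at correlation 0, and 6.28 + 5.57 = 11.9 at correlation 1. A 1-SD gap with 30% versus 10% loss then gives 0.20 × 8.4 = 1.7 to 0.20 × 11.9 = 2.4 points. Entry is limited to scores of 35 or below, so the trial's SD could differ from the pilot's.

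**5. Effect on the test.** These figures use SD 6.28 and treat the completers as two equal groups of 29 or 38. With no true effect, a bias of +1.26 raises the two-sided 2.5% error to about 7% (29 per group) or 9% (38 per group). With a true 5-point effect, a bias of −1.26 lowers power to about 51% or 64%, against 78% or 89% with the same loss and no bias.

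**The case against.** The strongest reply is that the plan says nothing about why patients leave, how many leave each arm, or what they would have scored. All of that stands, and it limits the point in these ways:

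- **Informative loss.** A reader might infer that the loss is known to depend on adherence. The documents do not say so; it is a reasonable inference from the nature of the outcome. Even then, the arm comparison is biased only if the loss or the gap differs between arms.
- **Direction.** A reader might infer that the guidance will look better than it is. The documents do not support one direction. Controls get no guidance or videos and might return less often. They are offered guidance at the end, but nothing ties that offer to returning the form.
- **Stopping treatment.** A reader might count patients who stop treatment as lost. No rule withdraws them; they can attend and score low, and one MARS-5 item asks about exactly this.
- **Complete cases.** Restriction to patients with a form is the default of the named tests, not a written rule. Nor is it stated whether the form is paper or electronic, so remote completion is unspecified rather than ruled out.
- **Worst case.** Losing exactly the lowest-scoring 20% of the intervention arm, with random loss in control, would give 0.350 × 6.28 = 2.2 points. Nothing in the documents makes so selective a pattern likely.

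It is also fair to say that the visits are part of outpatient care for patients with uncontrolled disease, which may help attendance, and that some who skip a visit will ignore a link. None of this supplies what is absent: a stated route to the scores of non-attenders and a stated set of patients to analyse.

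**Conclusion.** The point holds as a cheap improvement, not as a demonstrated bias. The primary score is tied to a visit, one patient in five is expected to be lost, and the only provision is a larger sample. The comparison is therefore exposed to a bias of unknown sign.

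For scale only: an assumed 30% versus 10% loss with a 6.28-point gap shifts the difference by 1.3 points up or down, a quarter to nearly a third of the target. A 1-SD gap on the 50-point total gives about 1.7 to 2.4 points. The bias is zero if loss and gap are the same in both arms. These sizes rest on an assumed split, an assumed gap and pilot SDs; the documents can neither confirm nor exclude them.

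**What to change.** In Material and method, state that:

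- at month 4 the MARS-5-N/L and the other questionnaires are sent by REDCap link or text message to every randomised patient who does not attend, or who has stopped the guidance or reminders, unless consent to data collection is withdrawn;
- the mode of completion (clinic or remote) is recorded.

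In the statistics section, state that all returned forms are analysed in the randomised arm and that non-return is reported by arm. Add one sensitivity analysis that varies the assumed score of non-returners separately in each arm, in both directions. Carrying the baseline score forward would not do this job: patients enter only at 35 or below, so some rise by regression to the mean is likely in both arms, and it would be denied to non-returners.

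The cost is a few sentences and an automated invitation, using phones and a platform the trial already has. The drawbacks are small: completion mode will be mixed, and some non-attenders will still not respond. As an illustration, if half of the missing forms were recovered, evaluable patients would rise from 37.6 to 47 × 0.9 = 42.3 per arm. If those recovered were typical of the non-attenders, the 30% versus 10% scenario would change as follows:

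- intervention: 0.30 × 6.28 − 0.15 × 6.28/0.85 = 0.78;
- control: 0.10 × 6.28 − 0.05 × 6.28/0.95 = 0.30;
- bias: 0.78 − 0.30 = about 0.5 points, instead of 1.26.

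### The primary between-arm analysis is not named: 4-month score or change is left open, and only unadjusted tests are listed although the first-visit score and gender stratum are available

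*Combined protocol and SAP*

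**What the plan says.** The section on statistics, data analysis and power calculation states: "The parametric data will be compared using paired and unpaired tests, and non-parametric data using Wilcoxon Signed-Ranks Test and Mann-Whitney Test, respectively". Chi-square is added for categorical variables. No test is tied to the primary outcome, and no adjusted or stratified analysis is mentioned.

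Other parts of the document point in different directions on what is analysed:

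- **Outcomes:** adherence "can be improved by 4 points after systematic and structured nursing guidance at the initial visit and controlled after four months". The yardstick is the arm without the guidance. This leans towards change and is a between-arm comparison.
- **Power calculation:** "With a MIREDIF of 5 and the largest SD of 6.28 by single measurement". This matches a comparison of scores at one time point. The same section also cites an intraindividual difference from a pilot study.
- **Threshold and scale:** "A P-value <0.025 is considered significant for a pooled MARS-5-N and MARS-5-L", where "the total score would be 25x2= a total of 50 points theoretically".

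The material for an adjusted analysis is already collected. Under Material and method: "Total MARS-5-N/L will be measured at their initial visit and four months after teaching or usual care", and "Randomization will be stratified by gender". The first-visit total is also an entry criterion (35 or less).

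**The concern.** A statistician given only this plan could not tell which p-value is the primary one. The unpaired t test and the Mann-Whitney test, each applied to the 4-month score or to the change, all fit the text. Each is sound if chosen beforehand. Left open, the choice can be made after seeing the data, and the 0.025 threshold then no longer controls the error rate.

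Either unadjusted choice is also a bet on a correlation that nobody has stated. A low correlation penalises the change score, and a high one penalises the 4-month score. Adjusting for the first-visit score avoids the bet.

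A smaller point concerns the paired and signed-rank tests. These work within an arm and cannot test the primary comparison. Patients enter on a low score, so both arms may rise with no effect of guidance. The plan does not say it would treat such rises as evidence of effect.

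**Working it through.** **1. The plan's own figure.** With difference 5, SD 6.28, two-sided alpha 0.025 and power 80%: n = 2 × 6.28² × (2.2414 + 0.8416)² / 5² = 29.99, so 30 per arm, and 30 × 1.2 = 36. The stated 36 is reproduced. It is the size for an unadjusted comparison of single scores. The SD of 6.28 belongs to MARS-5-L alone; that is a separate issue.

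**2. Inputs for comparing the analyses.** Pilot means (SDs) from Material and method are 20.4 (6.28) for lung and 20.7 (5.57) for nose, so the mean total is 41.1. The lung–nose correlation r is not given. Total SD S = √(6.28² + 5.57² + 2r × 6.28 × 5.57) = 8.39 (r = 0), 10.27 (r = 0.5), 11.85 (r = 1). The correlation ρ between first visit and four months in unselected patients is not given either; 0.3 to 0.8 is assumed. The pilot values 5.34 and 2.62 are not used for ρ, because the document gives them in opposite roles in two places.

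**3. Entry cut at 35.** In a normal model truncated at 35, 23–30% of patients are eligible, the first-visit mean is 30.1 to 27.5, and the first-visit SD is 4.06 to 6.11. Let v be this truncated variance.

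**4. Variance per patient.**

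- ANCOVA: S²(1 − ρ²)
- 4-month score: S²(1 − ρ²) + ρ²v
- Change: S²(1 − ρ²) + (1 − ρ)²v

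The variances below are for S = 10.27, v = 26.74. The ratios cover S from 8.39 to 11.85.

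| ρ | ANCOVA | Score | Change | Score / ANCOVA | Change / ANCOVA |
|---|---|---|---|---|---|
| 0.3 | 95.95 | 98.36 | 109.06 | 1.02–1.03 | 1.13–1.14 |
| 0.5 | 79.08 | 85.77 | 85.77 | 1.08–1.09 | 1.08–1.09 |
| 0.6 | 67.48 | 77.11 | 71.76 | 1.13–1.15 | 1.06–1.07 |
| 0.8 | 37.96 | 55.08 | 39.03 | 1.42–1.47 | 1.03 |

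A ratio of 1.08 means the unadjusted test needs 8% more patients for the same precision. The two unadjusted tests are equal at ρ = 0.5. At 0.3 the change test needs 10–11% more patients than the score test; at 0.8 the score test needs 38–43% more than the change test.

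**5. Cost of two covariates.** (1 + 2/(2n − 5)) × (t(0.9875, 2n − 4) / t(0.9875, 2n − 2))². At n = 30: 1.0364 × (2.3033/2.3011)² = 1.038. At n = 39: 1.028. Dividing the ratios by 1.038 gives net 0.985–1.42 against the score test and 0.988–1.10 against the change test. Against whichever unadjusted test is better at a given ρ, the net runs from 0.985 to about 1.05.

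**6. Effect of the cap at 50.** Simulation with scores rounded and cut at 10 and 50, 30 per arm, 20,000 trials, ρ 0.3/0.6/0.8:

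- Type I error at nominal 2.5% was 2.4–2.6% (score), 2.3–2.6% (change), 2.4–2.6% (ANCOVA) and 2.5–2.7% (ANCOVA on ranks).
- Gross gains were 2–47% over the score test and 3–20% over the change test.
- Power for 5 points at SD 10.27 was 35–61% (score), 30–78% (change), 36–78% (ANCOVA) and 35–74% (ANCOVA on ranks).

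A bounded beta model gave gains of 2–38% and 2–20%.

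**7. Leaving the choice open.** In the capped model (30 and 39 per arm, ρ 0.3/0.5/0.8), the smaller p-value of the score and change t tests has an error rate of 3.6–4.4%. With the Mann-Whitney versions also open it is 4.2–5.3%. A plain normal model with no entry cut (ρ 0.3/0.5/0.7) gives 4.6–4.7% and 5.4–5.6%.

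**8. Rise with no effect.** (1 − ρ) × (41.1 − first-visit mean) = 7.7–9.6 points at ρ = 0.3 and 2.2–2.7 at ρ = 0.8. The capped check gives 2.1–8.5 and the beta model 3.3–14.5.

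**The case against.** The strongest reply is that two claims of unequal weight are joined here. The failure to fix the analysed variable is plain from the text. The preference for ANCOVA rests on a modest gain: against the better unadjusted test the net is only about −1.5% to +5%. The 47% gross figure (42% net) needs both a correlation of 0.8 and a score test, and the outcome wording leans towards change. This stands, so the large figure should not lead the argument. The case for ANCOVA is that it is never far from the best, and nobody can say beforehand which unadjusted test would be.

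The list can also be read more kindly: data type decides between parametric and rank tests, and the outcome is stated against control, which points to an unpaired test or Mann-Whitney. That narrows the gap but leaves score versus change open, along with a switch that depends on the observed distribution.

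Further points that stand:

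- The choice is wider than score or change. The second sample-size calculation uses proportions (100% versus 80%), so a responder analysis is another candidate. Halving alpha for two questionnaires hints at separate lung and nose tests.
- The capped and beta checks give wider ranges than the plain normal model.
- The expected rise assumes the pilot patients resemble those screened, which the documents do not say. Text reminders in both arms are another reason for a rise.
- The inflated error rate describes conduct that the plan does not propose.

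None of these supplies the missing primary analysis.

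**Conclusion.** The concern holds, as a gap in pre-specification and an avoidable loss of precision. It does not make the planned comparison biased: each unpaired test, fixed in advance, keeps its level. The missing definition is certain from the text. The size of the precision gain is uncertain, because it rests on an assumed correlation of 0.3 to 0.8, a total SD built from the two pilot SDs, and a normal model with entry at 35 or less. On those assumptions ANCOVA risks at most about 1.5% of efficiency and can save much more if the unadjusted test chosen proves the wrong one. No gain is claimed for gender. The plan should be changed on this point; confidence in the size of the benefit is medium.

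**What to change.** Amend the statistics section as follows:

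- **Primary analysis:** ANCOVA of the 4-month pooled MARS-5-L/N score on arm, first-visit pooled score and gender. Report the adjusted difference with a confidence interval that matches the alpha (97.5% if 0.025 two-sided is kept).
- **Sensitivity analysis:** because the score is capped at 50, the same model on ranks of the 4-month and first-visit scores. State that the ANCOVA stays primary whatever distribution is observed.
- **Other candidates:** say what role, if any, the 80% responder comparison and separate lung and nose tests have, so that they are not alternative primaries.
- **Questionnaire secondaries:** the same model with the matching first-visit score.
- **Within-arm changes:** descriptive only.
- **Sample size:** do not reduce it on account of the adjustment.

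The cost is wording. ANCOVA is available in the SPSS software already named. Each covariate takes one degree of freedom, about 4% of precision in total at 30 completers per arm and about 3% at 39, already deducted in the net figures. No patients or visits are added.

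### The 0.025 threshold is justified by two questionnaires but applied to one test of their pooled score, so the plan must say whether it has one primary test or two

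*Combined protocol and SAP*

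**What the plan says.** The section on statistics, data analysis and power calculation gives one significance rule for adherence: "A P-value <0.025 is considered significant for a pooled MARS-5-N and MARS-5-L". It then describes that score as two scales of 25 points added together.

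The same paragraph explains the threshold in its sample-size sentence: "0.025% (0.05/2) because there are two schedules". The inputs there are "With a MIREDIF of 5 and the largest SD of 6.28 by single measurement" and 80% power, giving 36 per group including 20% dropout. A second calculation, 100% against 80% adherence, gives 39 per group, or 47 with dropout.

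Elsewhere the measure is treated as one total:
- The Purpose section defines adherence on MARS-5-L/N, "where the maximum score is 50 at 100% adherence for both diseases".
- The Outcomes section names one primary outcome, on MARS-5-N/L.
- The entry limit of 35 points can only refer to a total, since each scale stops at 25.
- The methods section gives its satisfactory-adherence mark, 41 points, for both scales together.

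No section specifies separate confirmatory tests of MARS-5-L and MARS-5-N.

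**The concern.** A Bonferroni split pays for having two chances to declare success. Once the two scores are added and compared between arms, there is one chance and nothing to split. Followed as written, the rule would call a primary result with p between 0.025 and 0.05 negative for a reason that does not apply to the test performed.

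The SD of 6.28 points the other way. It is the pilot SD of MARS-5-L alone, so the sample-size sentence reads like a calculation for two separate single-scale tests, while the decision rule is for one pooled test. If the choice is left until results are known, the primary conclusion could depend on which reading is adopted.

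**Working it through.** **Inputs from the plan.** Difference 5; SD 6.28; power 80%; alpha 0.05/2 = 0.025; dropout 20%. Pilot SDs come from the methods section: "In a pilot study, mean (SD) 20.4 (6.28) is found for MARS-5-L, and for MARS-5-N mean 20.7 (5.57) is found". Sidedness is not stated. The correlation between the two scales is not given.

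**Step 1: reproduce 36 per group.** n = 2(z_alpha + z_power)² SD² / difference².
- Two-sided 0.025: 2(2.2414 + 0.8416)² x 6.28² / 5² = 29.99, so 30. Then 30 x 1.2 = 36, an exact match.
- Two-sided 0.05 (numerically the same as one-sided 0.025): 2(1.9600 + 0.8416)² x 6.28² / 5² = 24.8, so 25. Then 25 x 1.2 = 30, or 25/0.8 = 31.25, so 32. No match.
- Literal 0.025% (0.00025, two-sided): 64.0005, so 65 before dropout. The percent sign is a slip.

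The 36 was therefore sized at two-sided 0.025. At 30 evaluable per arm the same formula returns 80.0% power, so the planned power is kept on these inputs.

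**Step 2: cost of the split on the plan's SD.** I use 39 evaluable per arm, the plan's larger pre-dropout figure. Two-sample t-test (noncentral t), difference 5, SD 6.28:
- alpha 0.025: 88.8%
- alpha 0.05: 93.5%
- loss: 4.7 points

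**Step 3: cost on a pooled-score SD (assumption).** The SD of the total is √(6.28² + 5.57² + 2 x r x 6.28 x 5.57), where r is the assumed correlation between MARS-5-L and MARS-5-N. Power at 39 per arm for 5 points, t-test:

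| Assumed r | SD of total | Power at 0.025 | Power at 0.05 | Loss (points) |
|---|---|---|---|---|
| 0 | 8.39 | 63.5% | 73.8% | 10.3 |
| 0.5 | 10.27 | 45.0% | 56.5% | 11.5 |
| 1 | 11.85 | 34.1% | 45.2% | 11.1 |

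Most of the fall from step 2 to step 3 comes from replacing a single-scale SD with a pooled one, which is a separate problem. Only the last column belongs to the alpha split.

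**Step 4: the two-primary reading.** If success on either scale were enough, two independent tests at 0.05 would give a familywise error of 1 − 0.95² = 9.75%. At 0.025 each it is 1 − 0.975² = 4.94%. The split is then appropriate, but the pooled rule is not the rule that uses it. If both scales had to succeed, no split would be needed.

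**The case against.** The strongest objection is that two primary tests were intended. The plan measures the two scales separately, reports a pilot mean and SD for each, sizes on a single-scale SD, splits alpha for two questionnaires, and adds a case in which both scales exceed 80%. On that reading 0.025 is right and the word pooled is the mistake. This stands as a possible reading, and it is why the point is not simply that alpha was wrongly halved. It does not rescue the text: the only stated decision rule is for the pooled score, and no pair of separate primaries is named. The case with both scales above 80% is not named as a primary test, and the split is not attributed to it.

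The second objection is that a strict threshold does no harm. It is true that it cannot raise the false-positive rate. It can still turn a positive primary result into a negative one.

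A reader might also infer that the split inflated the sample size. The documents do not support that. The step from 25 to 30 per arm exists only if a single-scale SD is kept for a pooled score. With a pooled-score SD of about 10.3 (assumed correlation 0.5), even alpha 0.05 needs 2(1.9600 + 0.8416)² x 10.27² / 5² = 66.2, so about 67 evaluable per arm, against the plan's 39. On the pooled reading the trial is too small, not too large.

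**Conclusion.** The point holds as an internal contradiction: the threshold and its stated reason belong to different designs, and one of them is wrong on either reading. It is a conservative error that should be corrected.

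The size is modest on the plan's own SD, 4.7 power points at 39 evaluable per arm. It is 10 to 12 points if the pooled SD lies between 8.4 and 11.9. That range assumes a correlation of 0 to 1 and that the pilot SDs apply to the enrolled patients.

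A reader might infer that the split itself drops the trial below its planned 80%. It does not, since the 36 was computed at 0.025; the loss is only relative to 0.05 at the same size. The alpha behind the 39 and 47 cannot be confirmed. An unpooled two-proportion formula at two-sided 0.025 gives (2.2414 + 0.8416)² x 0.16 / 0.04 = 38.02, so 39. A 4-point difference with SD 6.28 at two-sided 0.05 gives 38.7, also 39.

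**What to change.** Choose one design and record the choice, with a date, before anyone sees outcome data by arm.

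1. **One primary test.** This fits the Purpose, the entry limit and the primary outcome, which all use the total. State a single between-arm comparison of the pooled MARS-5-L plus MARS-5-N total at two-sided 0.05, with the two scales as supportive. Restate the power for the fixed sample size using the SD of the pooled score.
2. **Two primary tests.** If these are really intended, name MARS-5-L and MARS-5-N as separate primaries at two-sided 0.025 each, and delete the pooled rule.

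In either case replace the printed 0.025% with 0.05 or 0.025 to match, and state that the test is two-sided.

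The cost is a change of wording plus, for the first option, one recalculation. That needs a pooled-score SD, which the pilot data can supply if both scales were recorded in the same patients. The change of threshold itself adds no patients or data collection, but the restated power may be well below 80% because of the separate SD problem and should be reported as it is.
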